1. LIST OF ABBREVIATIONS

Item	Description
5D-ASC	5-Dimensional Altered States of Consciousness Rating Scale
AE(s)	Adverse events
ALP	Alkaline phosphatase
ALT / SGPT	Alanine aminotransferase / Serum glutamic pyruvic transaminase
AST / SGOT	Aspartate aminotransferase / Serum glutamic-oxaloacetic transaminase
AUC _{0-t}	Area under the concentration-time curve (AUC) from time zero (i.e., dosing time) to the time of the last quantifiable concentration.
AUC _{0-∞}	The AUC from time zero extrapolated to infinity using linear regression.
AUDIT	Alcohol Use Disorders Identification Test
BP	Blood pressure
BPI	Brief Pain Inventory
bpm	Beats per minute
BUN	Blood urea nitrogen
°C	Centigrade (temperature)
CBF	Cerebral blood flow
CEQ	Challenging Experience Questionnaire
C _{max}	Maximum observed concentration
C-SSRS	Columbia Suicide Severity Rating Scale
DEA	Drug Enforcement Administration
DMN	Default mode network
DMT	N,N-Dimethyltryptamine
DSM-5	Diagnostic and Statistical Manual of Mental Disorders – 5 th edition
DSMB	Data Safety Monitoring Board
DUDIT	Drug Use Disorders Identification Test
eCRF	Electronic case report form
ECG	Electrocardiogram
EDC	Electronic data capture
EoT	End of Treatment (visit)
°F	Fahrenheit (temperature)
FDA	Food and Drug Administration
fMRI	Functional magnetic resonance imaging
GCP	Good Clinical Practice
GAD-7	Generalized Anxiety Disorder 7-Item Scale
GGT	Gamma-glutamyl transferase
hCG	Human chorionic gonadotropin

CONFIDENTIAL

HIPAA	Health Insurance Portability and Accountability Act
HR	Heart rate
HRV	Heart rate variability
ICF	Informed Consent Form
IRB	Institutional Review Board
IUD	Intrauterine device
LDH	Lactate Dehydrogenase
LEC-5	Life Events Checklist for DSM-5
LSD	Lysergic acid diethylamide
LTFU	Long-term follow-up visit (~90 days / 3 months)
m ²	Meter squared
MAO	Monoamine oxidase inhibitors
MCH	Mean corpuscular hemoglobin
MCV	Mean corpuscular volume
MEQ30	Mystical Experience Questionnaire – Revised
mg	Milligram
min(s)	Minute(s)
mL	Milliliter
NCI CTCAE	National Cancer Institute's Common Terminology Criteria for Adverse Events
NIH HEALS	Healing Experience of All Life Stressors
PCL-5	PTSD Checklist for DSM-5
pH	Concentration of hydrogen
PHQ-9	Patient Health Questionnaire-9
pK	Pharmacokinetic
POMS	Profile of Mood States
PRN	Pro re nata (as needed)
PRO	Patient reported outcome
PTSD	Post-traumatic stress disorder
QoL	Quality-of-Life
QT (interval)	ECG measured: Q-wave to T-wave time duration
RBC	Red blood cell
RR	Respiration rate

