Unless a finding is made that excludes a participant from the trial, they will be evaluated by appropriately trained assessors for multiple psychological factors and assessments (including the LEC-5 and the PCL-5), some of which will determine the participant's eligibility as well as establish baseline measures for comparison pre- and post-treatment of exploratory objectives.

Participants will be required to complete several self-assessment quality-of-life (QoL) and patient reported outcome (PRO) instruments. They also will be provided with a health tracking wearable device to monitor several variables such as total daily steps, sleep parameters as well as heart rate and blood pressure. [If a participant already owns a suitable health tracking wearable device, they may use their own instead of the device provided for the trial.]

Participants that qualify for treatment will undergo individual preparatory training wherein each participant will be assigned to trained facilitators to build trust and rapport and receive education on the potential effects of psilocybin mushrooms. A Lead Therapist also will conduct a group education session regarding the treatment and take part in a ceremony following the individual preparation session.

Participants will be asked to bring their pain medication to the study site on Study Day 1, the dosing day. They will be educated on how the pain will be managed and they will not be prohibited from being administered additional pain medication should their pain increase following administration of the study drug. Patients who use opioid analgesics will be instructed to maintain their usual regimen.

- To the extent possible, input will be obtained from the participant's regular clinical providers on appropriate pain management for the participant during the trial, particularly in the case of analgesics associated with adverse reactions of concern with psilocybin (e.g., QTc prolongation with methadone).

During the screening period if a participant is found to have serious anxiety attack or another psychotic episode then the participant is referred to the relevant psychiatrist or responsible physician for follow up and treatment. Additionally, if the participant develops any medical emergency he/she will be managed as per the procedures described in detail under section 9.5.

Treatment Period:

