5.1.2 Exclusion Criteria

1. Currently uncontrolled hypertension. ($>140/90$ at Screening and $>145/95$ on Study Day 1).
2. History of recent seizure (within 3 months of Study Day 1).
3. History of stroke or transient ischemic attacks.
4. Preexisting history of valvulopathy or pulmonary hypertension.
5. A marked prolongation of QT interval (i.e., $QT \geq 450$ msec) over a series of 3 ECGs performed within 5-6 minutes.

CONFIDENTIAL

6. Currently uncontrolled diabetes ($HbA1c > 8.0\%$).
7. Potential for adverse drug-drug interactions such as the use of centrally-acting serotonergic agents within 24 hours prior to and for 72 hours following study drug administration on Study Day 1.
8. Significant suicide risk defined by (1) suicidal ideation as endorsed on items 4 or 5 on the Columbia Suicidal Severity Rating Scale (C-SSRS) within the last 6 months, at Screening, or at Baseline (Visit 1), or; (2) suicidal behaviors within the last 12 months as assessed by C-SSRS.
9. Patients with severe anxiety and depression measured as following: Participants with scores of 15 & above on Generalized Anxiety Disorder-7 (GAD-7) scale, and/or with scores of 20 & above on Patient Health Questionnaire-9 (PHQ -9).
10. Are pregnant or nursing or are women of childbearing potential who are not practicing a highly effective means of birth control.
11. Have any allergies or contraindication to psilocybin mushrooms.
12. Current users of psilocybin, LSD, DMT, Ayahuasca, Peyote, mescaline, and ketamine over the past 30 days will not qualify for the study unless the use of these agents is stopped for 30 days prior to Study Day 1 and the participant agrees to not use these (or similar) agents for 30 days after Study Day 1.
13. Are not able to attend face-to-face visits at the study site or plan to move out of the area prior to the 3-month LTFU visit.
14. Have any current problem that, in the opinion of the Investigator or Medical Monitor, might interfere with an individual's participation in the study or confound the assessment of safety and/or efficacy of the study drug.

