One-to-One			X ¹⁵						
Group Session			X ¹⁵	X	X				
Ceremony				X					
GAD-7 ⁹		X		X	X	X	X	X	X
PHQ-9 ¹⁰		X		X	X	X	X	X	X
NIH-HEALS		X		X	X		X	X	X
BPI		X		X	X	X	X	X	X
C-SSRS ¹¹		X		X	X	X	X	X	X
POMS ¹²				X					
SDS		X						X	
WCS				X			X	X	
MEQ30-revised				X				X	
CEQ				X				X	
5D-ASC				X					
AUDIT ¹³		X						◆	X
DUDIT ¹³		X						◆	X
Adverse Events					X	X	X	X	X

CONFIDENTIAL

Footnotes:

1. Pre-Screen: Study site staff should obtain verbal consent to collect information to assess potential eligibility for the trial. If the individual does not qualify or chooses not to participate, the information collected will be deleted, save for more general, non-identifiable, information recorded on the Screening Log.
2. Height / Weight: Height and weight should be measured at Screening, but only weight will be measured at the Study Day 8 and EoT visits, respectively.
3. Physical Examination: The physical exam should be targeted to head, eyes, ears, nose, throat (HEENT), abdomen and extremities. A brief neurological exam also should be performed on cranial nerves 2 through 12 as well as assessments of motor reflexes and cerebellar function.
4. Vital Signs: Measure body temperature, pulse oximetry (SpO₂), heart rate, respiratory rate, and blood pressure
5. Urine Pregnancy: A urine sample should be collected for all females of childbearing potential. If needed, a serum-HCG test can be done to confirm an initial positive result.
6. Clinical Laboratory Tests: Blood samples will be collected to perform clinical laboratory evaluations. A urine sample, for urinalysis, only will be collected at Screening.
7. Electrocardiogram: A 12-lead ECG should be obtained. If there is a finding of QT interval prolongation (i.e., > 450 msec), then triplicate ECG recordings should be done within 5 (to 6) minutes for confirmation. If confirmed, the participant is not eligible to participate in the trial.
8. Pharmacokinetic: Blood samples for PK testing should be obtained at the following timepoints on Study Day 1: up to 30 minutes prior to study drug administration and then at the following timepoints after dosing — 30 minutes (±2 mins), 60 minutes (±5 mins), 90 minutes (±5 mins), 120 minutes (±5 mins), 4 hours (±15 mins) and 8 hours (±15 mins)
 - ^ To qualify for treatment, participants must self-report at least one traumatic event via the LEC-5 that the clinician considers causative for a diagnosis of PTSD; in addition, they must score at least 33 on the PCL-5

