- If, upon examination, there are questions raised about possible medical problems, the investigator can request an additional review of the participant's medical records and order additional tests or assessments, as indicated.
- Assess eligibility criteria. If the participant meets all initial screening criteria, site staff will schedule the treatment visit for Study Day 1.
- Obtain participant's ring size and dispense the health tracking wearable device and provide instruction on its use (including daily wear, recharging, etc.). If a participant has the same (or compatible) device, they can use their own.
- Each participant will take part in an introductory psilocybin preparatory session with trained staff after confirming eligibility at the initial Screening visit and prior to Study Day 1. During these sessions, participants will engage in discussions with trained facilitators about any goals or desires they have, spiritual beliefs, or world views, and any beliefs about death or the afterlife. Participants also will be asked about their intentions with the psilocybin session.

The trained staff will inform participants of what to expect during their psilocybin-assisted session. Participants will be provided with (i) information about psilocybin mushrooms, (ii) expected psychoactive and physical effects, and (iii) methods for documenting and managing side effects of psilocybin mushrooms, if/when they occur.

Information also will be shared about community support, breathing strategies, as well as rescue psychotherapy or medications available to use if needed.

- Each participant will also participate in a group education session conducted by the lead therapist regarding the treatment and ceremony following the individual preparation session.
- Participants will be instructed to bring their pain medication with them on Study Day 1 and will be educated on how their pain will be managed, including having the study site provide additional pain medication should their pain increase after the 3 doses of whole organic psilocybin chocolate are self-administered.
 - Participants who use opioid analgesics will be instructed to maintain their usual regimen.
 - Input will be obtained from the participant's regular clinical providers on appropriate pain management for the participant during the trial, particularly in the case of

CONFIDENTIAL

analgesics associated with adverse reactions of concern with psilocybin (e.g., QTc prolongation with methadone).

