Study Medication Administration

Provided the participant remains eligible, they will undergo a symbolic ceremony in which intentions are set and then be instructed to self-administer the study drug.

- The participant will self-administer, under observation, a whole, dried, ground organic psilocybin mushroom (RTT1121 also called JMF-01) which has been milled and formulated into 3 solid chocolates.
 - A physician will be onsite, or if observing via video conferencing can reach the study site within 10 minutes in case of a medical emergency.

Post-Dose Monitoring and Assessments

Following the self-administration of the single dose of study drug, participants will be instructed to lie down wearing eyeshades and listen to a preselected music playlist via headphones and speakers. Participants will be closely monitored for medical and psychological (including psychosis) adverse effects to ensure their safety and well-being. Participants also will be assessed via clinician rating scales.

In addition to the therapists (and group) support provided, a trained therapy dog also will be available in the dosing room to offer additional support, if requested by the participant.

- Vital signs are to be measured every 30 minutes for at least 8 hours following study drug administration.
 - If vital signs are abnormal at 8 hours, the participant will remain at the study site for continued observation until the measurements return to baseline values, or the Investigator deems that not further monitoring is needed. Vital sign measurements listed below may be considered abnormal; (however, the Investigator may override these values):
 - Blood pressure above 140/90 mmHg
 - Heart rate outside the range of 50-90 beats per minute
 - Respiratory rate
 - Pulse oximetry – SpO2 ratio $< 92\%$
- Blood samples for PK profiling will be collected at the following timepoints
 - 30 minutes (± 2 mins)

CONFIDENTIAL

- 60 minutes (± 5 mins)
- 90 minutes (± 5 mins)
- 120 minutes / 2 hours (± 5 mins)
- 4 hours (± 15 minutes)
- 8 hours (± 15 minutes)
- Manage participant's complaints of pain and administer pain medication as warranted and record the type(s) and amount(s) administered.
- Nearing the 8-hour timepoint, the following clinician rating scales and participant QoL and PRO instruments should be administered and/or completed by the participant, respectively:
 - GAD-7
 - PHQ-9
 - C-SSRS
 - MEQ30-revised
 - CEQ
 - 5D-ACS
 - WCS
 - BPI

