9.4. Criteria for Termination or Suspension of the Study

The study will be fully enrolled and completed as planned unless one or more of the following criteria are satisfied that require temporary suspension of the study.

- New information regarding the safety or efficacy of the study drug indicates a significant change in the known risk/benefit profile for the drug, such that the risk is no longer acceptable for subjects participating in the study.
- Significant violation of Good Clinical Practice (GCP) that compromises the ability to achieve the primary study objectives or compromises subject safety.
- Study-specific criteria for suspension of the study:
 - The study will be paused if:
 - One participant experiences any of the following during the treatment phase of the trial starting at the time of study drug administration and through Study Day 30/ EoT, even if the participant prematurely discontinued further involvement in the trial:
 - A CTCAE Grade 3 – 5 toxicity which is possibly or probably related to study treatment,
 - A suicide attempt,
 - A marked prolongation of QT interval (i.e., $QT \geq 450$ msec) over a series of 3 ECGs performed within 5-6 minutes,
 - A serious episode of psychosis as determined by the Investigator that requires immediate medical attention,
 - A severe, non-serious, AE possibly related to study treatment,
 - Two participants experience: One or more serious AE's possibly or probably related to study treatment.

The study might also be terminated by the sponsor for the following reasons:

- Slow patient enrollment,
- Data collected lacking quality,
- Poor adherence to protocol,
- Other findings that could lead to the study not meeting its objectives.

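### The 450 msec limit for entry and for the one-participant study pause is set on uncorrected QT, so between 50 and 90 bpm it stands for a QTcF anywhere from 423 to 515 msec

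*Protocol*

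**What the plan says.** The limit appears in four places.

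- **Entry:** Synopsis exclusion 6 and section 5.1.2 item 5 exclude "A marked prolongation of QT interval (i.e., $QT \geq 450$ msec) over a series of 3 ECGs" taken within a span of 5 to 6 minutes.
- **Confirmation:** Table 1, footnote 7 says: "If there is a finding of QT interval prolongation (i.e., > 450 msec), then triplicate ECG recordings should be done". A confirmed finding makes the participant ineligible.
- **Study pause:** Section 9.4 repeats the limit of 450 msec or more, "over a series of 3 ECGs performed within 5-6 minutes", among the events that pause the study when a single participant has one between dosing and Day 30.

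Section 1 defines the QT interval as "ECG measured: Q-wave to T-wave time duration", which is the uncorrected interval. No correction formula is named anywhere. QTc appears only in sections 4.1 and 7.1.3, on pain management, where provider input is sought about "analgesics associated with adverse reactions of concern with psilocybin (e.g., QTc prolongation with methadone"). Section 7.1.3 also states: "Participants who use opioid analgesics will be instructed to maintain their usual regimen". The eligibility criteria contain no heart-rate limit.

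**The concern.** A fixed limit on raw QT confounds repolarisation time with heart rate. Above 60 bpm it is more lenient than the same number applied to QTc, and below 60 bpm it is stricter. The one QT-related drug risk the protocol names is expressed as QTc, so the stated concern and the gate are on different scales.

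Three things are at stake in a trial whose primary objective is safety and whose primary endpoints include clinically significant ECG abnormalities:

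- A participant with a long corrected interval and an ordinary or fast heart rate can be dosed, possibly while continuing an opioid with a QTc effect.
- A participant with a slow heart rate and a QTcF below 450 msec can be turned away.
- The one-participant pause can be set off by a slower heart rate alone, or missed because of a faster one.

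The operators also disagree. Footnote 7 requires more than 450 msec, while the exclusion and pause rules require 450 or more over three ECGs. A reading of exactly 450 therefore meets the limit but does not call for the triplicates needed to confirm it.

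**Working it through.** The protocol gives no derivation of 450 msec, so there is no figure to reproduce. The check converts the limit to a rate-corrected scale.

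**Inputs**
- Limit: QT 450 msec, uncorrected (section 5.1.2 item 5; section 9.4; section 1 for the definition).
- Heart rates: 50 to 90 bpm. Section 7.1.4 says a participant's post-dose vital signs may be considered abnormal with "Heart rate outside the range of 50-90 beats per minute". This range is borrowed to illustrate ordinary rates and is not an entry bound.
- Correction: Fridericia, QTcF = QT / RR^(1/3), with RR = 60/HR in seconds. This is the reviewer's choice, because the protocol names none.

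**What the limit means at each heart rate**

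At 50 bpm, RR = 60/50 = 1.2 s and QTcF = 450 / 1.2^(1/3) = 450 / 1.0627 = 423.5. At 90 bpm, RR = 60/90 = 0.6667 s and QTcF = 450 / 0.6667^(1/3) = 450 / 0.8736 = 515.1. The last column inverts the formula: raw QT = 450 × RR^(1/3).

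| HR (bpm) | QTcF when raw QT = 450 | Raw QT when QTcF = 450 |
|---|---|---|
| 50 | 423.5 | 478.2 |
| 55 | 437.1 | 463.2 |
| 60 | 450.0 | 450.0 |
| 70 | 473.7 | 427.5 |
| 80 | 495.3 | 408.9 |
| 90 | 515.1 | 393.1 |

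**Misclassification relative to QTcF 450 (whole msec)**
- Passes entry with QTcF of 450 or more: raw QT 428–449 at 70 bpm (QTcF up to 473), 409–449 at 80 bpm (up to 494), 394–449 at 90 bpm (up to 514).
- Meets the limit with QTcF below 450: raw QT 450–478 at 50 bpm, 450–463 at 55 bpm.

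**The pause rule**

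Tables 1 and 2 schedule ECGs at Screening, Day 1 pre-dose and Day 8, so Day 8 is the only scheduled post-dose ECG. Two cases with assumed values:
- QTcF stays at 430 and the rate falls from 60 to 52 bpm. Raw QT goes from 430 to 430 × (60/52)^(1/3) = 451.0. If the triplicates agree, the study pauses although repolarisation has not changed.
- QTcF rises from 430 at 60 bpm to 480 at 80 bpm. Raw QT is 480 × (60/80)^(1/3) = 436.1. Neither triplicates nor a pause under the QT rule follow.

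**Sensitivity to the formula**

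For raw QT 450 over 50 to 90 bpm, Bazett gives 411 to 551, Framingham 419 to 501 and Hodges 433 to 503. The direction is the same under each. At 90 bpm Bazett and Fridericia differ by 551 − 515 = 36 msec, so writing QTc without a formula would not settle the limit.

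**The case against.** The text and the arithmetic are not in dispute. The case against concerns practical weight.

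- **The range is borrowed.** The 50 to 90 bpm range belongs to the post-dose vital-sign rule, and the investigator may override it. This stands, and the range is used here only as illustration. With no heart-rate limit at entry, the real spread could be wider.
- **The size is a property of the formula.** The figures 423 and 515 follow for any trial using raw QT 450, and nothing shows that a participant at either extreme is likely. This also stands: the number reclassified cannot be estimated, because the protocol gives no QT or heart-rate distribution.
- **The pause half is weaker.** Section 2.3.2 gives a psilocin half-life of about 108 minutes and complete excretion within 24 hours, so a Day 8 change is hard to read as an acute drug effect. A false pause also needs someone below 450 at entry to cross it later. Both points narrow the pause consequence but leave entry untouched.
- **Other safeguards exist.** Provider input on analgesics, investigator discretion (section 5.1.2 item 14) and the pause for a related Grade 3–5 or severe event could each catch a case. None sets a QT limit at entry, section 4.1 seeks provider input only as far as possible, and a QTcF of 480 would not necessarily be reported as a severe event.
- **The exclusion came from the regulator.** The amendment history lists the QT exclusion among changes made at FDA request. It does not say that the correction was to be omitted, so this bears on the route of change only.
- **The operator mismatch is editorial.** It affects only a reading of exactly 450, and it adds little weight.

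**Conclusion.** The concern holds and should be fixed. As written, the rule misclassifies in both directions, and the clearer consequence is at entry: at 80 bpm a raw QT of 449 msec, which is a QTcF of 494, passes the numeric gate and the participant is dosed. The same limit on the pause rule has the same defect, but its practical reach is narrower because Day 8 is the only scheduled ECG that can trigger it.

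Confidence is high that the limit is on uncorrected QT and that its meaning changes with heart rate, since four standard corrections agree on direction. The exact range of 423 to 515 msec rests on Fridericia and on 50 to 90 bpm. How many of the 24 participants are affected is unknown. Eligibility and pause rules are protocol content already fixed here, so a later analysis plan would not repair them.

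**What to change.** State the limit as QTcF, name Fridericia's formula, and use one operator in synopsis exclusion 6, section 5.1.2 item 5, Table 1 footnote 7 and section 9.4. Record heart rate and QTcF from the 12-lead ECGs already scheduled at Screening, Day 1 pre-dose and Day 8.

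The sponsor's medical lead should confirm the number. Keeping 450 as QTcF tightens the rule for everyone above 60 bpm (raw QT about 409 msec at 80 bpm and 393 at 90) and loosens it below 60 bpm. The tightening could raise screen failures, with only about 30 people expected to be screened for 24 treated (section 7.1.1), and would also make the pause more sensitive at faster rates.

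The cost is a protocol amendment that goes back to the FDA and the IRB, because the present exclusion was added at FDA request. Operationally it adds one derived value per ECG and no new procedure.
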